4.4 Safety Objectives

- To test the safety and feasibility of a 30-minute bicycle exercise in hyperglycemic patients
- To test the safety of an intensive lifestyle intervention within 3 months following study enrollment

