5.2 Secondary Outcomes

Secondary outcomes are as follows:

- Absolute HbA1c reduction per stratification group (groups consist of HbA1c > 14 %, HbA1c < 14 % and > 10 % and HbA1c < 10 %)
- Change of HbA1c at 6 and 12 months after enrollment compared to control group
- Proportion of patients achieving target per stratified group after 3 and 6 months without anti-diabetic medication other than Metformin
- Changes in pH, base excess and bicarbonate 90 minutes after bicycle exercise compared to baseline
- Change of weight at 3, 6 and 12 months after enrollment compared to baseline and to standard of care
- Changes in blood glucose at the end of, as well as 30 and 90 minutes after bicycle exercise compared to baseline
- Feasibility of bicycle exercise at study enrollment in the ER, defined as absence of problem reports through the study team (e.g. patient cooperation)
- Safety of bicycle exercise, defined as:
 - o Absence of SAEs during the exercise
 - o No signs of acute cardiopulmonary decompensation in the patient during bicycle exercise
 - o No necessity to prematurely terminate the bicycle intervention because of other health or safety concerns
- Safety of intensive lifestyle intervention within 3 months following study enrollment, with the following endpoints:
 - o Number of SAEs in the intervention group compared to the control group
 - o Number of rescue medication administered in the intervention group compared to the control group
- Length of initial hospitalization, as well as number and length of re-hospitalizations and unplanned re-consultations within 3 months after initial consultation
- Changes in physical activity at 6 months compared to baseline assessed by SIMPAQ questionnaire (Endpoint: hours of physical activity)
- Changes in physical activity at 3 and 6 months compared to baseline assessed by actigraph (Endpoint: Stepgoal reached)
- Number of anti-diabetic medication at 30, 60, 90 days, as well as 6 months and one year compared to baseline in both arms
- Proportion of patients receiving insulin therapy after 6 months and one year in the intervention group compared to the control group
- Absolute health-care related costs at 3, 6 and 12 months in both arms
- Quality of life at 6 months in the intervention group compared to standard of care as assessed by SF-36 questionnaire.

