9.1.3.2 Laboratory Parameters

Laboratory parameters to be monitored for patient safety will be blood glucose, glycated hemoglobin A1c, pH, bicarbonate and base excess.

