9.1.5 Visit 1: Day 0 – Initial Consultation

All Patients will be recruited at the ER department or outpatient clinic of a participating study center or by their personal practitioner after presenting with a newly diagnosed or untreated type 2 diabetes mellitus. The treating physician will assess whether the patient is clinically fit to participate in the study and will order an ECG if necessary.

If the patient meets all of the inclusion and none of the exclusion criteria, he or she is required to sign the ICF. The patient will then be randomized 1:1 to the intervention or the control group.

Medical history is taken followed by a physical examination and drawing of blood samples for a venous blood gas analysis (pH, pCO₂, base excess, bicarbonate, glucose) and a baseline HbA1c (may be up to 14 days old).

Patients allocated to the intervention group will then perform a 30-minute bicycle exercise at 60 % of the age-adjusted maximal heart rate. Blood samples will again be drawn at the end of the exercise as well as 30 and 90 minutes after its completion to determine blood glucose levels and to do a venous BGA at 90 minutes after the bicycle exercise.

All participants of the intervention group will receive a structured plan for an intensive lifestyle intervention for the following 3 months as well as an actigraph provided by the DSBG to monitor daily physical activity between study visits.

Patients allocated to the control group will receive the standard diabetes care practiced at the study center according to national and international guidelines.

Patients will be discharged when clinically stable and no comorbidities require further hospitalization.

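### The bicycle-safety outcome counts SAEs and decompensation only during the 30-minute ride, although sampling continues until 90 minutes after it

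*Protocol*

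**What the plan says.** Section 4.4 of the protocol sets as a safety objective: "To test the safety and feasibility of a 30-minute bicycle exercise in hyperglycemic patients". Section 5.2, repeated almost word for word in the synopsis, turns this into a secondary outcome with three components:

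- "Absence of SAEs during the exercise"
- "No signs of acute cardiopulmonary decompensation in the patient during bicycle exercise"
- "No necessity to prematurely terminate the bicycle intervention because of other health or safety concerns"

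Section 9.1.5 describes the day. The ride lasts 30 minutes, and then: "Blood samples will again be drawn at the end of the exercise as well as 30 and 90 minutes after its completion". Glucose is measured at each of these times and a venous blood gas at the last one.

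Section 9.1.3.2 states: "Laboratory parameters to be monitored for patient safety will be blood glucose, glycated hemoglobin A1c, pH, bicarbonate and base excess". In 5.2 the acid-base values form a secondary outcome of their own, "Changes in pH, base excess and bicarbonate 90 minutes after bicycle exercise compared to baseline", and glucose after exercise forms another. Neither is mentioned in the bicycle-safety definition. Sections 11.1.3 and 11.1.5 plan descriptive statistics for safety and refer back to 5.2, so they do not widen the window.

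**The concern.** Harm from a bout of exercise need not appear before the patient stops pedalling. The protocol allows for this by continuing to sample for 90 minutes, but the outcome that answers the safety objective stops with the ride. A patient who decompensates ten minutes after a completed ride meets all three criteria for safe.

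The background says that safety in the emergency room has still to be shown, and the risk/benefit section looks ahead to wider use in that setting. Readers will therefore take a favourable result as covering the ride and its immediate aftermath. The definition supports only the first. The error has one direction: the short window can omit events but cannot add any.

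**Working it through.** The protocol states no sample size, threshold or rate for this outcome, so there is no plan figure to reproduce. The check sets the time window of each component against the sampling schedule.

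**Schedule (section 9.1.5), minutes from the start of exercise**

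- Ride: 0 to 30
- Glucose at the end of exercise: 30
- Glucose 30 minutes later: 30 + 30 = 60
- Glucose and blood gas 90 minutes after the ride: 30 + 90 = 120

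Section 11.1.3 counts from the start of exercise and gives the same times, 60 and 120 minutes.

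**Reach of each component (section 5.2)**

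- SAEs: minutes 0 to 30, by the word *during*.
- Acute cardiopulmonary decompensation: minutes 0 to 30, by the same word.
- Premature termination: only before the intervention is complete. The general study design section describes the bicycle intervention as a session of about two hours. Even on that wider reading, a patient who has finished the ride cannot have it cut short.

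Share of the sampled period covered: 30 / (30 + 90) = 30 / 120 = 25%. Left out: 90 minutes.

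**Where an event at, say, minute 45 would go**

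- *SAE*: into the general SAE documentation with causality assessment (sections 10 and 10.1.1) and into the 3-month SAE comparison between arms, which 5.2 lists as safety of the lifestyle intervention. It enters no bicycle-safety component.
- *Non-serious decompensation or other AE*: into AE recording, which Table 1 schedules at Visit 1. It enters no bicycle-safety component. It could reach another 5.2 endpoint only indirectly, for example through rescue medication or an unplanned consultation.
- *Fall in pH, bicarbonate or base excess*: into the separate acid-base outcome, summarised in 11.1.3 by median, interquartile range, graph and Wilcoxon signed-rank test. It does not enter the bicycle-safety outcome.

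**Effect of one event**

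With 62 patients randomised 1:1, 62 / 2 = 31 are allocated to the ride. If all ride and none has an event under the present definition, the safety rate is 31/31 = 100%. One event after the ride that was counted would make it 30/31 = 96.8%, a change of 1/31 = 3.2 percentage points.

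**Would a count of any acid-base decrease help?**

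Suppose nothing truly changes and each of the three values is equally likely to rise or fall (an assumption). The chance that at least one is lower lies between 50%, if the three move together, and 1 − 0.5³ = 87.5%, if they are independent. Such a count would flag at least half the patients on noise alone.

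**The case against.** The strongest reply is that little is lost. Post-exercise acid-base and glucose changes are pre-specified outcomes. Section 11.1.3 plans spread, graphs and a paired test as well as medians, and individual listings are the kind of detail an SAP may hold. AEs are collected on the day of the ride and SAEs from consent onward. Each SAE receives a causality assessment in which timing is a criterion, and one that may be attributable to the intervention goes to the ethics committee within 15 days. The outcome is descriptive, in a proof-of-concept trial, and no test or decision rests on it.

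All of that stands, and it rules out several stronger readings:

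- A reader might infer that acid-base worsening disappears from the results. It does not; it is reported under another bullet.
- A reader might infer that a post-ride SAE could never be linked to the ride. The event-level causality assessment provides for this, although its template wording refers to a drug.
- A reader might infer that non-serious events are counted nowhere. Section 9.1.3.1 places them under safety assessment; they are absent only from the bicycle-safety components.
- A reader might take 25% as the share of risk covered. The protocol gives no event rate over time, so it is only a share of minutes.
- A reader might infer that patients are under observation for the full 90 minutes. The protocol states sampling; section 9.1.3.4 states staff presence only for the exercise.

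The objection does not remove the gap in the outcome definition. That definition is fixed in the protocol, and it is what will be quoted as the answer to the safety objective.

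**Conclusion.** The point holds in limited form. As written, the bicycle-safety outcome measures safety during the ride. An SAE or decompensation in the 90 minutes to the last scheduled sample does not count against it, and the resulting bias can run only towards safe. Section 9.1.3.2 treats acid-base values as safety parameters while the safety definition in 5.2 does not refer to them, so the two should be reconciled.

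The likely size cannot be given, because the protocol states no rate of post-exercise events. Each uncounted patient would shift the rate by 3.2 percentage points if all 31 allocated patients ride. The primary endpoint and its analysis are unaffected. This is an inexpensive improvement to one descriptive secondary outcome, not a threat to the trial's main result.

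**What to change.** In section 5.2 and the synopsis, define the window for the SAE and decompensation components as running from the start of exercise until the 90-minute post-exercise sample. Leave the premature-termination component as it is. Beside the safety outcome, present each patient's baseline and 90-minute pH, bicarbonate and base excess descriptively. Do not add a count of any decrease, which would mostly reflect measurement noise; no clinical threshold is proposed here.

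If the present wording is kept, limit the conclusion to safety during the exercise and reconcile sections 4.4, 5.2, 9.1.3.2 and 9.1.5 accordingly.

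The cost is wording and one listing. No blood sample or visit is added. Because the protocol does not state observation up to 90 minutes, the sponsor should confirm that events in that interval will be recorded with their time, so that they can be assigned to the window. The reported safety rate may come out slightly less favourable.

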We believe it is crucial to stress the importance of lasting lifestyle changes for metabolic control from the very point of diagnosis. Intervention early in the course of the disease often suffices to control metabolic dysregulation and may even have a durable impact. However, as mentioned above, multiple reasons including non-compliance as well as doubt about the efficacy of sport and diet changes compared to drugs make a lasting change in lifestyle difficult. Furthermore, most patients with type 2 diabetes remain asymptomatic for a prolonged period of time, leaving patients in doubt about the immediate benefit of lifestyle changes. Often, untreated type 2 diabetes manifests itself for the first time with symptoms of polyuria and polydipsia. This offers a unique opportunity to demonstrate the potential of lifestyle changes. However, in daily practice, symptomatic patients with polyuria and polydipsia are typically referred to an emergency room and are treated with drugs and hospitalized. With this study, we therefore aim to implement lifestyle intervention as first line treatment in new onset type 2 diabetes patients. We expect to achieve a durable educational impact with this approach and to increase the patients' motivation for glycemic control through healthy lifestyle while keeping pharmacological aids at a minimum.

Investigational Product (Treatment, Device) and Indication

No investigational products are used in this trial.

Preclinical Evidence

Not applicable.

Clinical Evidence to Date

Refer background and rationale.

Explanation for Choice of Comparator (or Placebo)

The control treatment used in this trial is based on the current standard of care for diabetes according to national and international guidelines (American Diabetes 2012). There is no medical disadvantage for the participants of the control group.

Risks/Benefits

Subjects will only be performing the bicycle exercise when they are found to be eligible by the responsible medical doctor with concern to their clinical status. During the remaining study period patients are encouraged to be physically active. This may increase the risk for physical activity associated accidents (i.e. adverse events) but does not represent a greater risk within the study compared to general physical activity in the normal population.

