9.1.3 Assessment of Safety Outcomes

9.1.3.1 Adverse Events

We consider the risks of this study to be very low. Possible risks may occur if glycemic control cannot be achieved and maintained with lifestyle intervention. Consequently, the patient may experience symptoms of hyperglycemia requiring further medical attention. Patients will be systematically questioned about the occurrence of AEs at each study visit. The patients' safety will be monitored by assessment of blood sample parameters and the recording and evaluation of all study related AEs.

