10.1.3 Follow Up of (S)AEs

All subjects who experience AEs will be followed until the event resolves or until the subject's participation in the study ends. For those AEs judged to be unrelated to the study intervention, the outcome at last observation will be recorded on the appropriate pages of the CRF.

Subjects experiencing AEs that were judged to be possibly, probably, or definitely related to a study

intervention will be followed until the events resolve or until the event is judged to be chronic or stable. Resolution of such events will be documented on the appropriate pages of the CRF.

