11.1.5 Safety Analysis

Descriptive analysis will be used. Please refer also to chapter 5.2

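### Lifestyle safety is measured only by SAEs and rescue medication, and the sections on recording adverse events conflict, so non-serious harms are asked about but belong to no safety outcome

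*Protocol*

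**What the plan says.** **Outcome.** Protocol 5.2 introduces the item as "Safety of intensive lifestyle intervention within 3 months following study enrollment, with the following endpoints" and lists two: "Number of SAEs in the intervention group compared to the control group" and "Number of rescue medication administered in the intervention group compared to the control group". Section 4.4 has the matching objective, with the same three-month window.

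**Analysis.** 11.1.5 reads: "Descriptive analysis will be used. Please refer also to chapter 5.2". 11.1.3 also says that safety outcomes, with a reference to 5.2, will be described.

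**Expected harms.** Section 3 (Risks/Benefits) says of encouraging activity: "This may increase the risk for physical activity associated accidents (i.e. adverse events". Section 9.1.3.1 adds that if glycaemic control fails under lifestyle treatment, "the patient may experience symptoms of hyperglycemia requiring further medical attention".

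**Recording.** Section 9.1.3.1 has patients questioned about AEs at every visit, but then rests safety monitoring on blood parameters and "the recording and evaluation of all study related AEs". The opening of section 10 commits to collecting SAEs. Section 10.1.3 goes further: "For those AEs judged to be unrelated to the study intervention, the outcome at last observation will be recorded".

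**The concern.** A trial that sets out to test the safety of an exercise programme should report the harms it expects from exercise. Here a sprain or fall that is not serious counts towards neither safety endpoint. The same is true of symptomatic hyperglycaemia that leads to no admission and no rescue drug. The report could call the intervention safe because no SAE occurred, without any safety outcome that describes the more likely events.

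The conflict over recording makes this worse. The trial is open label (6.1.2). If only study-related events are recorded, an unblinded judgement of relatedness decides what enters the database. Control patients receive standard care and no study intervention, so few of their events could be called study related. That could remove most control-arm AEs, and with them the comparison.

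**Working it through.** **1. Which outcome can hold a non-serious event?**

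| Event, non-serious | SAE count (5.2) | Rescue medication (5.2) | Unplanned re-consultation (5.2) |
|---|---|---|---|
| Activity-associated injury | no | no | only if the patient consults; cause not recorded |
| Symptomatic hyperglycaemia, rescue drug started | no | yes | if the patient consults |
| Symptomatic hyperglycaemia, no rescue drug | no | no | only if the patient consults; cause not recorded |

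The re-consultation outcome stands apart from the safety items in 5.2, and 11.1.3 analyses it as a count and length of stay. It cannot separate an injury from any other reason to see a doctor.

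**2. Which events are to be recorded?**

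| Place | Scope |
|---|---|
| Tables 1 and 2 | AE row in both arms: visits 1 to 7 for the intervention arm; 1, 6 and 7 for controls |
| Section 6, General Study Design | adverse events acquired at follow-up in both groups |
| 9.1.3.1 | questioning on AEs at each visit, but recording and evaluation of study-related AEs |
| Section 10, opening | SAEs |
| 10.1.3 | AEs of any relatedness; outcome of unrelated AEs goes on the CRF |
| 12.1.2 | AEs listed as source data separately from SAEs |

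The restriction in 9.1.3.1 cannot be applied together with 10.1.3. The opening of section 10 does not exclude non-serious AEs, but it does not commit to them either.

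**3. How much can the SAE count say?** The protocol states no figure on this point. The only input is the planned total of 62 randomised 1:1, so 62/2 = 31 per arm.

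- If no SAE is seen in 31, the one-sided 95% upper bound is 1 − 0.05^(1/31) = 9.2% (10.1% with 28 patients).
- The chance of seeing no SAE in an arm is (1 − p)^31: 73% at p = 1%, 53% at 2%, 20% at 5%, 4% at 10%. These rates are assumed.

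**4. How many non-serious events might be left out?** The protocol gives no rate, so the risk p of a non-serious activity injury or symptomatic hyperglycaemia is assumed over a range. Expected patients = 31p; chance of at least one = 1 − (1 − p)^31.

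| Assumed p | Expected of 31 | Chance of at least one |
|---|---|---|
| 5% | 1.6 | 80% |
| 10% | 3.1 | 96% |
| 20% | 6.2 | 99.9% |

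This shows only that such events would be seen if they occur at these rates. Some of the hyperglycaemia cases would still reach the rescue count.

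**5. What would a table show?** Exact 95% intervals are 2.0% to 25.8% for 3/31 and 7.5% to 37.5% for 6/31. A two-sided Fisher test with 31 per arm has power of 2% for 10% versus 5% and 26% for 20% versus 5%. Description with intervals is therefore right, and a test would add little.

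**6. Is enquiry equal between arms?** No. After enrolment and up to day 90, intervention patients are asked at visits 2 to 6, five times, and controls only at visit 6 (Tables 1 and 2; 9.1.6). Intervention patients also have weekly coaching calls.

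**The case against.** A reader might infer that the expected harms will go unreported, or that none of them could enter a 5.2 outcome. The documents do not support this.

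- The protocol attributes both harms to the intervention. In that arm they would count as study related and be recorded even under the narrow wording of 9.1.3.1.
- AEs are asked about in both arms, graded by CTCAE (10.1.1) and kept as source data.
- In the intervention arm, symptomatic hyperglycaemia triggers reassessment and standard care (section 8, Dose/Device Modifications), so many cases may appear as rescue medication.
- Either harm may prompt an unplanned consultation, which is collected in both arms and compared between them.

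All of this stands. It limits the point to what is missing: a safety outcome that holds these events, and one consistent recording rule.

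It can also be said that 11.1.5 refers *also* to 5.2, so it need not confine the analysis to those outcomes, and that AE tables are usually left to a statistical analysis plan, which is not shown. That is fair for the table layout. But the outcome list and the recording rule belong to the protocol. A later table can use only what sites were told to record, and at present they are told different things.

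**Conclusion.** The point holds in a limited form. Non-serious AEs are asked about in both arms under conflicting recording rules, but they are not a safety outcome. The analysis sections name only the 5.2 outcomes. Activity injuries without a consultation enter no 5.2 outcome at all. Hyperglycaemia does so only partly and indirectly.

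The size depends on assumed rates: about 2 to 6 of 31 intervention patients at risks of 5% to 20%, less those whose hyperglycaemia leads to a rescue drug. The SAE count cannot fill the gap, since zero events in 31 is compatible with a true rate of up to 9.2%. The loss of control-arm AEs is a risk only if sites follow the 9.1.3.1 wording; under 10.1.3 it does not arise.

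The primary endpoint and its analysis are unaffected. The change is still worth making, because a stated safety objective is otherwise answered only in part.

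**What to change.** 1. Reconcile 9.1.3.1 and the opening of section 10 with Tables 1 and 2, 10.1.3 and 12.1.2, so that all AEs are recorded in both arms regardless of seriousness or relatedness. Record relatedness as a separate field.
2. Add to 5.2 and 11.1.5 a descriptive outcome: number and percentage of patients per arm with at least one AE from enrolment to day 90, and separately with an activity-associated injury and with symptomatic hyperglycaemia, each with an exact 95% confidence interval.
3. Count every event with onset up to day 90, whichever visit recorded it. A table built only from the day 90 enquiry would drop intervention-arm events already recorded at visits 2 to 5 and so favour the intervention. Show which intervention-arm events were first recorded at those visits, and state that the more frequent enquiry limits the between-arm comparison.
4. Treat day 180 data as supplementary, since they lie outside the three-month safety window.

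This needs no new visit and changes no treatment rule. The cost is wording in four places, some extra CRF entries for unrelated events, one descriptive table, and a reported safety profile that may look slightly less favourable.
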